3.1 Differences Statement

Study M14-347 is a Phase 3 open-label clinical study to evaluate the long-term efficacy, safety, and tolerability of adalimumab in the treatment of adult subjects with CD who participated in and successfully completed Study M14-115. Subjects will receive adalimumab 40 mg every other week (eow) with the opportunity to dose escalate to adalimumab 40 mg every week (ew), if the subject meets the criteria for inadequate response as defined in [Table 1](#).

3.2 Benefits and Risks

Extensive clinical and post marketing experience exists with adalimumab in a wide range of disease states including CD and ulcerative colitis (UC). The safety profile of adalimumab in those indications is well-established with more than 50,000 patient years of adalimumab clinical trial experience. The clinical studies in adult CD have not altered this safety profile and demonstrated a positive benefit/risk balance. Conditions which may present a risk specifically for patients with CD are exclusion criteria in this study (e.g., evidence of colonic dysplasia or active infections).

3.3 Adalimumab Overview

Adalimumab is a recombinant human immunoglobulin (IgG1) monoclonal antibody containing only human peptide sequences. Adalimumab is produced by recombinant deoxyribonucleic acid (DNA) technology in a mammalian cell expression system. It consists of 1,330 amino acids and has a molecular weight of approximately 148 kilodaltons. Adalimumab is composed of fully human heavy and light chain variable regions, which confer specificity to human tumor necrosis factor (TNF), and human IgG1

heavy chain and kappa light chain sequences. Adalimumab binds with high affinity and specificity to soluble TNF- α but not to lymphotoxin- α (TNF- β).

TNF is a naturally occurring cytokine that is involved in normal inflammatory and immune responses. Elevated levels of TNF play an important role in pathologic inflammation. Adalimumab binds specifically to TNF and neutralizes the biological function of TNF by blocking its interaction with the p55 and p75 cell surface TNF receptors. Adalimumab also modulates biological responses that are induced or regulated by TNF. After treatment with adalimumab, levels of acute phase reactants of inflammation (C-reactive protein [CRP] and erythrocyte sedimentation rate) and serum cytokines rapidly decrease.

Adalimumab was first approved in US and EU for the treatment of rheumatoid arthritis (RA) in 2002 and 2003, respectively. Additional indications have been approved in the US and EU including psoriasis, psoriatic arthritis, axial spondylitis, CD, juvenile arthritis and UC. Additional updates regarding approved indications can be found in the current edition of the Humira Investigational Drug Brochure.

3.4 Safety information

Adalimumab therapy has a well-established and well described safety profile in adults based on extensive post marketing experience and continued clinical trial patient exposure since the first approved indication in 2002 for RA. A detailed discussion of the pre-clinical toxicology, metabolism, pharmacology and safety experience with adalimumab can be found in the current Investigator's Brochure. AbbVie is committed to continue to collect safety information including those events that may occur in this trial in order to confirm this established safety profile and to identify any unknown potential adverse reactions, rare events and those events with a long latency. AbbVie is participating in a FDA-requested, TNF inhibitor class wide exploration of the rare appearance of malignancy in patients who are 30 years of age or younger at the time of diagnosis. The risk of malignancy in this age group has not been established and is difficult to study due to its rarity. AbbVie appreciates your attention to the additional

reporting requirements needed in this unlikely event, outlined in Section [6.5](#) under Adverse Event Reporting.

4.0 Study Objectives

The primary objective of this study is to evaluate the long-term efficacy, safety, and tolerability of repeated administration of adalimumab in subjects with CD who participated in and successfully completed Study M14-115.

The secondary objective is to assess PK and immunogenicity of adalimumab following subcutaneous (SC) administration.

5.0 Investigational Plan

5.1 Overall Study Design and Plan: Description

This is a Phase 3, multicenter, open-label extension (OLE) study which comprises a 40-week open-label period designed to evaluate the long-term efficacy, safety, and tolerability of adalimumab. Approximately 300 adult subjects who participated and successfully completed Study M14-115 and who meet all of the inclusion criteria and none of the exclusion criteria will be eligible to enroll into this study.

Subjects will be evaluated for entry into Study M14-347 at the final study visit (Week 12) of Study M14-115. A subject's participation in the study is anticipated to be up to 40 weeks. There is a \pm 3-day window for all study visits. An effort will be made to bring the subject back to their original study visit (calculated from Week 0) if they are out of the visit window.

Study visits for clinical and safety assessments will be performed at Weeks 0, 8, 16, 24, 32 and 40/Premature Discontinuation (PD). All subjects will be provided with a paper subject diary in which they will record CD-related symptoms (number of liquid or very soft stools, abdominal pain rating, general well-being) and adalimumab dosing information throughout the study. Blood samples will be collected at various time points for routine labs, along with hs-CRP, adalimumab serum concentrations, anti-adalimumab

antibody (AAA) levels and other biomarker analyses. In addition, stool samples for calprotectin and microbiota will be collected. The stool samples should be taken before starting bowel preparations for endoscopy. Endoscopic evaluation will be performed at Week 40/PD, if the PD occurs after Week 24. CDAI evaluations will be calculated based on entries recorded into the subject's diary at all study visits. The SFPS (Stool [liquid/soft] Frequency + Abdominal Pain Score) will be calculated using the weighted values for the CDAI components "Number of liquid or very soft stools" and "Abdominal pain."

The Week 12 visit of Study M14-115 will be considered Week 0 (Baseline) of Study M14-347. All subjects will receive open-label adalimumab 40 mg every other week (eow) beginning at Week 0. No dose will be administered at Week 40. Subjects may be escalated to adalimumab 40 mg every week (ew) at or after Week 1 should the subject meet the criteria for inadequate response ([Table 1](#)).

Table 1. Inadequate Response

Response Type	Definition
Inadequate response	Crohn's disease activity index (CDAI) of ≥ 200 at any one visit and at least one of the following criteria is met: an increase of at least 1 mg/L in level of high-sensitivity C-reactive protein (hs-CRP) from Baseline or an hs-CRP ≥ 5 mg/L. The hs-CRP results used to determine inadequate response can be from the prior or current visit. Assessment of inadequate response should include consideration by the Investigator to rule out symptoms caused by reasons other than Crohn's disease related inflammation.

[figure not shown]
For subjects taking corticosteroids at Baseline of Study M14-115 adalimumab dose escalation should be considered in lieu of increases in steroid dose. Subjects who continue to experience inadequate response on 40 mg ew who were taking corticosteroids at Baseline of Study M14-115 may have their steroid dose increased, per the Investigator's discretion, in order to manage the subject's symptoms. Any subject who continues to experience inadequate response on 40 mg ew may be discontinued from the study at the investigator's discretion after discussion with the study designated physician (SDP). Subjects who dose escalated to adalimumab 40 mg ew, have one opportunity to de-

escalate adalimumab dose to 40 mg eow provided the following criteria have been met: CDAI < 200 and high-sensitivity C-reactive protein (hs-CRP) value equal to or lower than that observed at the time of dose escalation. Subjects who experience inadequate response after dose de-escalation (using the same criteria outlined above), may again be escalated to 40 mg ew. A subject has only **one** opportunity to dose de-escalate and one opportunity to re-escalate to ew adalimumab dosing.

Changes in adalimumab dosing may only occur when the above criteria are met but are not mandatory.

A schematic for dose adjustments is presented in [Figure 1](#).

[figure not shown]
Figure 1. Dose Adjustment Algorithm

Subjects may discontinue adalimumab treatment at any time during study participation (Section 5.4). Subjects will be discontinued from the study if they withdraw consent or if they are deemed unsuitable to continue for any reason by the Investigator. Subjects who end study participation early will have a PD visit. All subjects will have a follow-up phone call approximately 70 days after the last administration of study drug to obtain information on any new or ongoing adverse events (AEs). The 70-day follow-up phone call will not be required for any subject who initiates commercial adalimumab.

A schematic of the study design is presented in [Figure 2](#).

Figure 2. Study Schematic

*Week 12 from M14-115

**Dose adjustment (see figure 1) can occur at Week 2 or any time thereafter if criteria for Inadequate response are met.

Clinical evaluation will be completed at each study visit. See activities outlined in [Table 2](#).

Throughout the study, subjects will only be allowed to change the dosage of CD-specific concomitant medications as specified below:

- Immunosuppressant doses may be decreased or terminated in the event of moderate-to-severe treatment-related toxicities.
- Subjects who are taking corticosteroid therapy at Baseline of Study M14-115 should continue the steroid taper initiated during Study M14-115. Increases in steroid doses back to the dose used at Baseline of Study M14-115 to manage inadequately controlled CD-related symptoms may be undertaken at the Investigator's discretion in subjects who are receiving adalimumab 40 mg ew. For subjects taking adalimumab 40 mg eow, adalimumab dose escalation

(for subjects who meet inadequate response criteria) should be considered in lieu of increases in the steroid dose.

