1.2 Synopsis

AbbVie Inc.	Protocol Number: M14-347
Name of Study Drug: Adalimumab	Phase of Development: 3
Name of Active Ingredient: Adalimumab	Date of Protocol Synopsis: 04 December 2014
Protocol Title: A Multicenter, Open-Label Study to Evaluate the Long Term Efficacy, Safety, and Tolerability of Repeated Administration of Adalimumab in Subjects with Crohn's Disease	
Objectives: The primary objective of this study is to evaluate the long-term efficacy, safety, and tolerability of repeated administration of adalimumab in subjects with Crohn's disease (CD) who participated in and successfully completed Study M14-115. The secondary objective is to assess pharmacokinetics (PK) and immunogenicity of adalimumab following subcutaneous (SC) administration.	
Investigators: Multicenter	
Study Sites: Only sites that have enrolled subjects from Study M14-115 will be included.	
Study Population: Subjects with CD who previously participated in and successfully completed Study M14-115.	
Number of Subjects to be Enrolled: Approximately 300 subjects who participated in and successfully completed Study M14-115.	
Methodology: This is an open-label extension (OLE) study which comprises a 40-week open-label period designed to evaluate the long-term efficacy, safety, and tolerability of adalimumab. Approximately 300 subjects with CD who participated in and successfully completed Study M14-115 will be enrolled. Subjects will be evaluated for entry into Study M14-347 at the final study visit (Week 12) of Study M14-115. Subjects must meet all of the inclusion criteria and none of the exclusion criteria to be eligible to participate in this study. The Week 12 visit of Study M14-115 will be considered Week 0 (Baseline) of Study M14-347. All subjects will receive open-label adalimumab 40 mg every other week (eow) beginning at Week 0. Subjects may be escalated to adalimumab 40 mg every week (ew) at or after Week 1 should the subject meet the criteria for inadequate response:	

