5.3.3.2 Additional Efficacy Variables

For additional efficacy endpoints, the baseline is defined as the Baseline in Study M14-115.

- Proportion of subjects with CDAI remission (CDAI $<$ 150) at Week 40 among subjects with CDAI remission at Week 0 of Study M14-347.
- Proportion of subjects with a SFPS remission (SFPS $<$ 50) at Week 40 among subjects with SFPS remission at Week 0 of Study M14-347.
- Proportion of subjects who achieve CDAI remission (CDAI $<$ 150) over time.
- Time in CDAI remission (CDAI $<$ 150) for subjects in CDAI remission at Week 0 of Study M14-347.
- Time to achieve CDAI remission (CDAI $<$ 150) for subjects who were not in CDAI remission at Week 0 of Study M14-347.
- Time to first dose escalation.

- Proportion of subjects who require weekly dosing at Week 1 of Study M14-347.
- Time to achieve SFPS remission (SFPS < 50) for subjects who were not in SFPS remission at Week 0 of Study M14-347.
- Time in SFPS remission (SFPS < 50) among subjects with SFPS remission at Week 0 of Study M14-347.
- Proportion of subjects who achieve a Simplified Endoscopic Score for Crohn's Disease (SES-CD \leq 4) with an Ulcerated Surface subscore no greater than 1 in any segment at Week 40.
- Proportion of subjects who achieve a SFPS < 50 over time.
- Proportion of subjects who entered Study M14-347 who were taking corticosteroids at Week 0 of Study M14-115 who discontinue corticosteroid use and achieved CDAI remission (CDAI < 150) at Week 40.
- Proportion of subjects who entered Study M14-347 who were taking corticosteroids at Week 0 of Study M14-115 who discontinue corticosteroid use at each visit.
- Proportion of subjects with CDAI response (decrease in CDAI \geq 70 points from Baseline) over time.
- Proportion of subjects with enhanced CDAI response (decrease in CDAI \geq 100 points from Baseline) over time.
- Proportion of subjects with endoscopic response (decrease \geq 50% SES-CD from Baseline) at Week 40.
- Proportion of subjects with Inflammatory Bowel Disease Questionnaire (IBDQ) response (decrease \geq 16 points from Baseline) over time.
- Proportion of subjects with IBDQ remission (IBDQ \geq 170 points) over time.
- Change in IBDQ from Baseline over time.
- Change from Baseline in fecal calprotectin level over time.
- Change from Baseline in hs-CRP level over time.
- Proportion of subjects with hs-CRP < 5 mg/L and fecal calprotectin < 250 μ g/g over time.

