4.2 Design Diagram

This is a Phase 3, multicenter, open-label extension (OLE) study which comprises a 40-week open-label period designed to evaluate the long-term efficacy, safety, and tolerability of adalimumab. 252 adult subjects who participated and successfully completed Study M14-115 Induction were enrolled into this study.

Subjects were evaluated for entry into Study M14-347 at the final study visit (Week 12) of Study M14-115. A subject's participation in the study was anticipated to be up to

40 weeks. There was a \pm 3-day window for all study visits. An effort was made to bring the subject back to their original study visit (calculated from Week 0) if they were out of the visit window.

Study visits for clinical and safety assessments were performed at Weeks 0, 8, 16, 24, 32 and 40/Premature Discontinuation (PD). All subjects were provided with a paper subject diary in which they could record CD-related symptoms (number of liquid or very soft stools, abdominal pain rating, and general well-being) and adalimumab dosing information throughout the study. Blood samples were collected at various time points for routine labs, along with hs-CRP, adalimumab serum concentrations, anti-adalimumab antibody (AAA) levels and other biomarker analyses. In addition, stool samples for calprotectin and microbiota were collected. The stool samples were taken before starting bowel preparations for endoscopy. Endoscopic evaluation were performed at Week 40/PD, if the PD occurred after Week 24. CDAI evaluations were calculated based on entries recorded into the subject's diary at all study visits. The SFPS (Stool [liquid/soft] Frequency + Abdominal Pain Score) were calculated using the weighted values for the CDAI components "Number of liquid or very soft stools" and "Abdominal pain."

All subjects received open-label adalimumab 40 mg every other week (eow) beginning at Week 0. No dose was administered at Week 40. Subjects might be escalated to adalimumab 40 mg every week (ew) at or after Week 1 should the subject met the criteria for inadequate response ([Table 1](#)).

[figure not shown]
Table 1. Inadequate Response

| Response Type | Definition |
|---------------------|---|

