| Inadequate response | Crohn's disease activity index (CDAI) of ≥ 200 at any one visit and at least one of the following criteria is met: an increase of at least 1 mg/L in level of high-sensitivity C-reactive protein (hs-CRP) from Baseline or an hs-CRP ≥ 5 mg/L. The hs-CRP results used to determine inadequate response can be from the prior or current visit. Assessment of inadequate response should include consideration by the Investigator to rule out symptoms caused by reasons other than Crohn's disease related inflammation. |

For subjects taking corticosteroids at Baseline of Study M14-115 adalimumab dose escalation was considered in lieu of increases in steroid dose. Subjects who continued to experience inadequate response on 40 mg ew who were taking corticosteroids at Baseline of Study M14-115 might have their steroid dose increased, per the Investigator's discretion, in order to manage the subject's symptoms. Any subject who continued to experience inadequate response on 40 mg ew might be discontinued from the study at the investigator's discretion after discussion with the study designated physician (SDP).

Subjects who dose escalated to adalimumab 40 mg ew, had one opportunity to de-escalate adalimumab dose to 40 mg eow provided the following criteria had been met: CDAI < 200 and high-sensitivity C-reactive protein (hs-CRP) value equal to or lower than that observed at the time of dose escalation. Subjects who experienced inadequate response after dose de-escalation (using the same criteria outlined above), might again be escalated to 40 mg ew. A subject had only one opportunity to dose de-escalate and one opportunity to re-escalate to ew adalimumab dosing.

Changes in adalimumab dosing might only occur when the above criteria were met but were not mandatory. A schematic for dose adjustments is presented in [Figure 1](#).

Figure 1. Dose Adjustment Algorithm

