Subjects might discontinue adalimumab treatment at any time during study participation (Section 5.4). Subjects would be discontinued from the study if they withdraw consent or if they were deemed unsuitable to continue for any reason by the Investigator. Subjects who ended study participation early would have a PD visit. All subjects were to have a follow-up phone call approximately 70 days after the last administration of study drug to obtain information on any new or ongoing adverse events (AEs). The 70-day follow-up phone call would not be required for any subject who initiated commercial adalimumab.

Clinical evaluation was completed at each study visit. See activities outlined in [Table 2](#).

Throughout the study, subjects were only allowed to change the dosage of CD-specific concomitant medications as specified below:

- Immunosuppressant doses might be decreased or terminated in the event of moderate-to-severe treatment-related toxicities.
- Subjects who were taking corticosteroid therapy at Baseline of Study M14-115 should continue the steroid taper initiated during Study M14-115. Increases in steroid doses back to the dose used at Baseline of Study M14-115 to manage inadequately controlled CD-related symptoms might be undertaken at the Investigator's discretion in subjects who were receiving adalimumab 40 mg eow.

For subjects taking adalimumab 40 mg eow, adalimumab dose escalation (for subjects who meet inadequate response criteria) were to be considered in lieu of increases in the steroid dose.

Table 2. Study Activities

| Activity | Baseline (Week 0) ^a | Week 8 | Week 16 | Week 24 | Week 32 | Week 40/ Premature Discontinuation | Unscheduled Visit ^k | 70-Day Follow-Up Call ^l |
|---|-----------------------------------|--------|---------|---------|---------|--|-----------------------------------|--|
| Informed Consent | X | | | | | | | |
| Inclusion/Exclusion ^b | X | | | | | | | |
| Medical/Surgery History Update ^b | X | | | | | | | |
| Previous and Concomitant Medication Update ^b | X | X | X | X | X | X | X | X |
| Vital Signs | X ^a | X | X | X | X | X | X | X |
| Endoscopy ^c | X ^a | | | | | X | | |
| SES-CD Score | X ^a | | | | | X | | |
| Physical Examination ^d | X ^a | X | X | X | X | X | X | X |
| Urinalysis ^e | X ^a | X | X | X | X | X | X | X |
| Pregnancy Test ^f | X ^a | | | | | X | | |
| Chemistry and Hematology ^h | X ^a | X | X | X | X | X | X | X |
| hs-CRP | X ^a | X | X | X | X | X | X | X |

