For categorical additional efficacy endpoints, the two-sided 95% confidence interval for the proportions will be provided. The NRI method will be used for subjects with missing data at the time point evaluated. The LOCF method will also be used as the sensitivity analyses.

For continuous additional efficacy endpoints, change from Study M14-115 Baseline will be summarized by descriptive statistics using mean, standard deviation, minimum, median and maximum. Both LOCF and observed case analyses will be performed.

For time to event additional efficacy endpoints, the number of event and the 25th, median, and 75th percentiles of time to event will be estimated by the product limit method. The 95% CI for the median time-to-event will also be provided if applicable.

The time to first occurrence of event will be calculated as (first occurrence of event date or censoring date – date of first dose of the treatment during this study + 1). Subjects who did not experience the event prior to discontinue or complete the study will be censored at the date the last assessment was taken. For the endpoint of time to dose escalation, subjects without experiencing an event will be censored at the last available dose date.

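### The steroid failure rule lets a never-escalated subject return to the pre-taper dose and still count as a responder; three wording slips also need errata

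*Protocol*

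**What the plan says.** **Steroid failure rule.** Protocol 5.2.3.2 and SAP 6.0 (CD-Related Concomitant Therapy) give the same two-limb rule. A subject becomes a non-responder from the event to study end if systemic corticosteroids not in use at M14-347 Baseline are started, or if the dose goes above the one taken at M14-115 Baseline. Protocol 5.1 tells subjects on steroids at M14-115 Baseline to continue the taper begun in that study.

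**Permitted increases.** Protocol 5.1 limits changes in Crohn's medication to those it lists. It allows a return to the M14-115 Baseline steroid dose "in subjects who are receiving adalimumab 40 mg ew". For subjects on every-other-week (eow) dosing it says that dose escalation should be considered instead. The SAP 4.2 narrative agrees ("Subjects who continued to experience inadequate response on 40 mg ew who were taking corticosteroids at Baseline"), but the SAP 4.2 bullet allows the increase "in subjects who were receiving adalimumab 40 mg eow".

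**Dose escalation.** SAP 6.0 makes anyone who escalates to weekly (ew) dosing a non-responder from then to study end.

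**Start of weekly dosing.** The Figure 2 note in Protocol 5.1 says adjustment "can occur at Week 2 or any time thereafter if criteria for Inadequate response are met". The Protocol synopsis says "at or after Week 1 should the subject meet the criteria for inadequate response", the text of Protocol 5.1 agrees, and SAP 4.2 says "at or after Week 1 should the subject met the criteria for inadequate response". Both documents list the endpoint "Proportion of subjects who require weekly dosing at Week 1 of Study M14-347". Protocol 5.5.1 describes dosing at Week 0 as eow or ew, whereas Section 5.1 starts everyone on eow.

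**The concern.** The two limbs of the steroid rule use different time points: on/off use at M14-347 Baseline for a start, and the pre-taper dose for an increase. The result can run the wrong way, because a small restart from zero is a failure while a larger rise from a low dose is not. The primary endpoint is the Week 40 proportion with endoscopic improvement among those improved at Week 0, in a single-arm open-label study. Steroid-supported responders in the numerator would inflate it, and there is no control arm to offset the effect.

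The wording slips matter less. A site that followed the Figure 2 note could contribute no event to the Week 1 weekly-dosing endpoint and no escalation time before Week 2. Read alone, the SAP bullet makes a steroid increase on eow look permitted.

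**Working it through.** The plan gives no figure to reproduce here: SAP 4.3 states that no sample size was calculated. The check applies the rules to cases.

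**Steroid rule.** Let B be the M14-115 Baseline dose, W the M14-347 Week 0 dose and N the new dose, in prednisone equivalents (SAP 6.0 table).

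- Failure if (W = 0 and N > 0) or N > B.
- No failure if W > 0 and N ≤ B.

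Illustration with B = 30 mg, the top class limit in SAP 7.3. The values of W and N are assumptions, because the documents give no individual doses and no taper schedule.

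| Subject | W | Change | Start limb | Increase limb | Status |
|---|---|---|---|---|---|
| A | 0 mg | restarts at 5 mg | met | 5 > 30: no | failure to study end |
| B | 5 mg | raised to 30 mg | not met | 30 > 30: no | possible responder |
| C | 5 mg, then stopped | restarts same steroid at 30 mg | not met, in use at Week 0 | 30 > 30: no | possible responder |

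The largest uncensored rise is B − W. With W = 5 mg (assumed) and B at the SAP 7.3 class limits:

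- B = 10: 10 − 5 = 5 mg
- B = 20: 20 − 5 = 15 mg
- B = 30: 30 − 5 = 25 mg

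After stopping, a restart of up to 10, 20 or 30 mg is uncensored.

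**Who is exposed on the primary endpoint.**

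1. Subjects with W = 0 are not exposed, since any restart fails.
2. Subjects who escalate are not exposed, since they are non-responders from that point, even if they later de-escalate.
3. What remains is never-escalated eow subjects with W > 0 and endoscopic improvement at Week 0. Protocol 5.1 lists no permitted steroid increase for them.
4. An uncensored rise needs 0 < N ≤ B, so B > 0. All exposed subjects fall in the yes stratum of the baseline corticosteroid subgroup in SAP 10.5.

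**Size per subject.** If n subjects have endoscopic improvement at Week 0, each counted responder who is reclassified lowers the proportion by 1/n. The documents do not give n. It cannot exceed the 252 enrolled (SAP 4.2), so the shift is at least 1/252 = 0.4 percentage points per such subject.

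**Start of weekly dosing.** SAP 10.3 computes time to event as the event date minus the "date of first dose of the treatment during this study + 1".

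- Week 1: 7 + 1 = Day 8
- Week 2: 14 + 1 = Day 15
- Difference: 7 days

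These are nominal days. With the ±3-day dosing window (Protocol 5.3.1.1), Week 1 spans Days 5 to 11 and Week 2 spans Days 12 to 18. The ranges do not overlap, so following the note would still rule out a Week 1 event.

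**SAP 4.2 bullet.** It conflicts with Protocol 5.1, with the SAP's own narrative, and with the sentence after it, which directs eow subjects towards escalation. The SAP 6.0 censoring rule depends on steroid dose and not on eow or ew, so the wrong word enters no derivation.

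**The case against.** The best defence is that the increase limb is coherent: Protocol 5.1 permits a return to the M14-115 dose, so the rule penalises only what goes beyond it. That explains the wording but does not help the primary endpoint. The permission covers ew subjects, who are already non-responders. The only subjects whose primary status the tolerance can change are those without the permission.

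Other safeguards exist, and each is partial:

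- The SAP 10.5 subgroup by baseline steroid use gives a no stratum free of the gap, but leaves the yes stratum and the overall result as they are.
- SAP 6.0 carries failures forward from M14-115, but only for events during that study.
- A steroid increase on eow would be a deviation to be notified under Protocol 7.0. However, SAP 5.1 defines only the ITT and Safety sets, which are identical, so no analysis set removes it.
- SAP 10.3 reports steroid discontinuation among Week 0 users, but this does not alter the primary numerator.

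Two limits stand. The example doses are assumed. The stop-and-restart case is clearest when the same steroid is resumed; a different steroid could be read as a new start and so as a failure.

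On the slips, the objection that the intended reading is clear is right. They are editorial.

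**Conclusion.** The steroid point holds as a modest design gap that is cheap to close. The number affected cannot be derived and is probably small. It is bounded by the number on corticosteroids at M14-347 Week 0, and for the primary endpoint further limited to those with endoscopic improvement at Week 0 who never escalated.

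A reader might infer more than the documents support:

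- *That the protocol and SAP contradict each other on steroid failure.* They do not; the rule is the same in both.
- *That the Figure 2 note makes the Week 1 endpoint 0% by construction.* That holds only for sites that followed the note over the synopsis and the text of Section 5.1. Escalation times come from recorded dates, and Protocol 5.5.1 even mentions ew at Week 0.
- *That the SAP eow bullet alters the analysis.* SAP 4.2 is a past-tense description of the design and feeds no derivation.
- *That rises of 25 mg occurred.* That figure is an illustration from an assumed Week 0 dose.

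None of the three slips changes Week 40 status.

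**What to change.** Keep the primary steroid rule. Count the subjects with endoscopic improvement at Week 0 who never escalated, were not censored under the present rule, and whose systemic steroid dose either rose above the M14-347 Week 0 dose (prednisone equivalent) or was restarted after stopping. Protocol 5.2.3.1 already requires dose and dates for all medications, so no new data are needed. If the count is zero, say so in the report. If not, add one sensitivity run of the primary endpoint in which such an increase or restart also starts the censoring.

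List as errata:

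- Figure 2 note: Week 2 to Week 1.
- SAP 4.2 steroid bullet: eow to ew.
- Protocol 5.5.1: align Week 0 dosing with the eow start in Section 5.1.

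The cost is three errata, one count and at most one extra run. The proportion in that run can only be equal or slightly lower, because the Week 0 denominator is fixed and failures are only added.
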